9.10. Other aspects

9.10.1. Reporting to the chief executive of the study site

Each investigator will report the following information to the chief executive at the study site:

PFIZER CONFIDENTIAL

CT24-WI-GL02-RF02 4.0 Non-Interventional Study Protocol Template For Secondary Data Collection Study 01-Jun-2022

- 1) Measurements to be revised in the protocol;
- 2) Progression of the study;
- 3) Termination, discontinuation, and interruption of the study.

10. PROTECTION OF HUMAN SUBJECTS

10.1. Patient information

All parties will comply with all applicable laws, including laws regarding the implementation of organizational and technical measures to ensure protection of patient personal data. Such measures will include omitting patient names or other directly identifiable data in any reports, publications, or other disclosures, except where required by applicable laws.

The personal data will be stored at the study site in encrypted electronic form and will be password protected to ensure that only authorized study staff have access. The study site will implement appropriate technical and organizational measures to ensure that the personal data can be recovered in the event of disaster. In the event of a potential personal data breach, the study site shall be responsible for determining whether a personal data breach has in fact occurred and, if so, providing breach notifications as required by law.

To protect the rights and freedoms of natural persons with regard to the processing of personal data, when study data are compiled for transfer to Pfizer and other authorized parties, patient names will be removed and will be replaced by a single, specific, numerical code, based on a numbering system defined by Pfizer. All other identifiable data transferred to Pfizer or other authorized parties will be identified by this single, patient-specific code. The investigator site will maintain a confidential list of patients who participated in the study, linking each patient's numerical code to his or her actual identity. In case of data transfer, Pfizer will maintain high standards of confidentiality and protection of patients' personal data consistent with the CSA and applicable privacy laws.

10.2. Patient consent

The investigator must obtain informed consent from the patients regarding the use of their medical records for this study as well as data provision to a third party prior to collecting the data for this study.

The informed consent form must comply with local regulatory and legal requirements. The informed consent form used in this study and any changes made during the course of the study must be prospectively approved by both the independent ethics committee (IEC) and by Pfizer.

10.2.1. For patients who are alive and continue to visit the study site

The investigator must obtain written informed consent from each patient before data collection. After obtaining written informed consent, the investigators must retain the original signed consent form for each patient. When obtaining the oral informed consent in consideration of the patient's condition or situation, the investigator will document the method and content of the explanation as well as the details of the obtained consent.

10.2.2. Patients who are alive and were transferred to another medical facility

Investigators must obtain oral informed consent for data collection from each patient who was transferred to another hospital before data collection. When obtaining oral informed consent, the investigator will document the method and content of the explanation as well as the details of the obtained consent.

When it is difficult to obtain oral informed consent for the following reasons, consent will not be required based on the Act on the Protection of Personal Information Article 27 (1) - (iii) and the Frequently Asked Questions related to the article:

- The study site does not obtain valid patient contact information.
- When considering the time available and research costs incurred in obtaining oral informed consent at the study site, it is concluded that obtaining oral informed consent at the study site could significantly impact the conduct of the study.

Even in these cases, the study information must be disclosed, and the patients' legally acceptable representatives will be guaranteed an opportunity to refuse to provide patient data to the sponsor.

10.2.3. Patients who are deceased

In accordance with Chapter 4 ("Informed Consent") of the "Ethical Guidelines for Life Science and Medical Research Involving Human Subjects," the study information needs to be disclosed, and the patients' legally acceptable representatives will be guaranteed an opportunity to refuse providing the patient's data to the sponsor.

10.2.4. Disclosing study findings to patients

Human genome and gene information will not be collected in this study. It is highly improbable that study results include incidental findings or secondary findings, and the disclosure of the study results to patient individually is not planned for this reason. The study results will be published in the manner described in "10.8 Registration and publication of study".

10.3. Patient withdrawal

10.3.1. Patients who are alive and continue to visit the study site, or were transferred to another medical facility

During the course of this study, the patient can withdraw consent at any time. In any circumstance, every effort should be made to document patient outcomes, whenever possible. If the patient disagrees, the patient's data will be removed from the study database. However, if published already, in such as within a congress presentation or in peer-reviewed manuscripts, the patient's data will not be removed.

10.3.2. Patients who are deceased

When patients' legally acceptable representatives refuse study participation on behalf of the deceased patient during the study period, all data must be removed from the dataset. If the results of this study had disclosed via publication or at a conference at the time of refusal, the patient's data cannot be removed.

10.4. Institutional review board (IRB)/Independent ethics committee (IEC)

There must be prospective approval of the study protocol, protocol amendments, and other relevant documents (eg, informed consent forms if applicable) from the relevant IRBs/IECs. All correspondence with the IRB/IEC must be retained. Copies of IRB/IEC approvals must be forwarded to Pfizer.

In addition, based on the Ethical Guidelines for Medical and Health Research Involving Human Subjects issued by the Ministry of Education, Culture, Sports, Science and Technology, the Minister of Health, Labour and Welfare, and Welfare and the Ministry of Economy, Trade and Industry, a multicenter study should be reviewed by the central IEC together. However, it is not prohibited for a review to be conducted by the individual IEC at each site.

10.5. Ethical conduct of the study

The study will be conducted in accordance with legal and regulatory requirements, as well as with scientific purpose, value and rigor and follow generally accepted research practices described in the “Ethical Guidelines for Life Science and Medical Research Involving Human Subjects” .

10.6. Predictable risks and benefits

This study is a retrospective chart review study. Therefore, participation in this study does not pose specific risks or benefits to individual patients.

10.7. Conflicts of interest

This study will be performed with funding from Pfizer Inc. The investigators will review any conflicts of interests that may affect the planning of this study or the interpretation of results through the IRB/IEC or the Conflicts of Interest Committee, according to the regulations of the study site. When the results of the study are published, accurate information will be disclosed through self-report, in compliance with the guidelines of the academic society or journal used for publishing the results of the study.

10.8. Registration and publication of study

Before implementation, this study will be registered at the ClinicalTrials.gov. The registered content will be properly updated without delay.

10.9. Secondary use of information obtained from subjects

The data obtained from this study may be used within other studies for different purposes, such as within another study linked to this study or an integrated analysis (meta-analysis) using other research data. Such use will only be possible if another protocol is developed and approved by the IRB/IEC. In such a case, information on the newly specified purpose of use, among other considers, shall be notified or disclosed to the subjects and the opportunity for refusal from the subjects, etc., shall be guaranteed, in principle, regarding the implementation of another study. In addition, the provision of information collected in this study to organizations or individuals outside of the parties responsible for this study shall be limited to cases in which Pfizer Inc. agrees. The ownership of rights, arising from secondary use or provision to external parties shall be determined through consultation with Pfizer Inc. and the parties to which the secondary use or provision of study data is made.

PFIZER CONFIDENTIAL

CT24-WI-GL02-RF02 4.0 Non-Interventional Study Protocol Template For Secondary Data Collection Study 01-Jun-2022

Furthermore, the possibility of future secondary use or external provision of the collected information will be explained to the participants at the time of their enrollment in this study, and informed consent will be obtained.

10.10. Responding to consultations from patients and other related parties

The investigator will set up a helpline for consultations with the patients and other related parties in regard to this study. Information about each site's helpline will be included in the informed consent form and in documents related to opt-outs.

11. MANAGEMENT AND REPORTING OF ADVERSE EVENTS/ADVERSE REACTIONS

This study protocol requires human review of patient-level unstructured data; unstructured data refer to verbatim medical data, including text-based descriptions and visual depictions of medical information, such as medical records, images of physician notes, neurological scans, X-rays, or narrative fields in a database. The reviewer is obligated to report adverse events (AEs) with explicit attribution to any Pfizer drug that appear in the reviewed information (defined per the patient population and study period specified in the protocol). Explicit attribution is not inferred by a temporal relationship between drug administration and an AE but must be based on a definite statement of causality by a healthcare provider linking drug administration to the AE.

The requirements for reporting safety events on the non-interventional study (NIS) adverse event monitoring (AEM) Report Form to Pfizer Safety are as follows:

- All serious and non-serious AEs with explicit attribution to **any Pfizer drug** that appear in the reviewed information must be recorded on the EDC (cubeCDMS[®]) and reported, within 24 hours of awareness, to Pfizer Safety using the NIS AEM Report Form.
- Scenarios involving drug exposure, including exposure during pregnancy, exposure during breast feeding, medication error, overdose, misuse, extravasation, lack of efficacy, and occupational exposure associated with the use of a Pfizer product must be reported, within 24 hours of awareness, to Pfizer Safety using the NIS AEM Report Form.
- For exposure during pregnancy in studies of pregnant women, data on the exposure to avelumab during pregnancy, are not reportable unless associated with serious or non-serious AEs.
- For these AEs with an explicit attribution or scenarios involving exposure to a Pfizer product, the safety information identified in the unstructured data reviewed is captured in the Event Narrative section of the report form, and constitutes all clinical information known regarding these AEs. No follow-up on related AEs will be conducted.

All the demographic fields on the NIS AEM Report Form may not necessarily be completed, as the form designates, since not all elements will be available due to privacy concerns with the use of secondary data sources. While not all demographic fields will be completed, at the very least, at least one patient identifier (eg, gender, age as captured in the narrative field of the form) will be reported on the NIS AEM Report Form, thus allowing the report to be considered a valid one in accordance with pharmacovigilance legislation. All identifiers will be limited to generalities, such as the

PFIZER CONFIDENTIAL

CT24-WI-GL02-RF02 4.0 Non-Interventional Study Protocol Template For Secondary Data Collection Study 01-Jun-2022

statement “A 35-year-old female...” or “An elderly male...” Other identifiers will have been removed.

Additionally, the onset/start dates and stop dates for “Illness,” “Study Drug,” and “Drug Name” may be documented in month/year (mmm/yyyy) format rather than identifying the actual date of occurrence within the month /year of occurrence in the day/month/year (DD/MMM/YYYY) format.

All research staff members must complete the following Pfizer training requirements:

- *“Your reporting responsibilities (YRR) Training for Vendors.”*

These trainings must be completed by research staff members prior to the start of data collection. All trainings include a “Confirmation of Training Certificate” (for signature by the trainee) as a record of completion of the training, which must be kept in a retrievable format. Copies of all signed training certificates must be provided to Pfizer. Re-training must be completed on an annual basis using the most current YRR training materials.

12. PLANS FOR DISSEMINATING AND COMMUNICATING STUDY RESULTS

The results of this study are not part of any regulatory submission. The results of this study will be submitted to conferences and/or peer-reviewed journals. The final output will be filed in Pfizer’s Global Document Management System upon final study completion.

In the event of any prohibition or restriction imposed (eg, clinical hold) by an applicable competent authority in any area of the world, or if the investigator is aware of any new information which might influence the evaluation of the benefits and risks of a Pfizer product, Pfizer should be informed immediately.

14. LIST OF TABLES

Table 1. Variables in this study

15. LIST OF FIGURES

None.

ANNEX 1. LIST OF STAND ALONE DOCUMENTS

”Implementation Structure in This Study” will be prepared independently.

Number	Document reference number	Date	Title
1	ANNEX 1	14 Oct 2022	Implementation structure of this study

ANNEX 2. ADDITIONAL INFORMATION

Not applicable

PFIZER CONFIDENTIAL

CT24-WI-GL02-RF02 4.0 Non-Interventional Study Protocol Template For Secondary Data Collection Study 01-Jun-2022

**VERSION HISTORY**

Version	Effective Date	Change Type (New, Revise, Admin)	Summary of Revisions
1.0	22-May-2023	New	-

PFIZER CONFIDENTIAL

CT24-WI-GL03-RF03 2.0 *Non-Interventional Statistical Analysis Plan For Secondary Data Collection*  
*Study 01-Jun-2020*  
Page 1 of 30

**1 AMENDMENTS FROM PREVIOUS VERSION(S)**

Not applicable

**2 INTRODUCTION****2.1 STUDY DESIGN**

*The present study is a multicenter, non-interventional, retrospective, medical chart review of patients with metastatic renal cell carcinoma (mRCC) who received avelumab plus axitinib as first-line therapy in Japan between December 20, 2019, and October 17, 2022.*

*The source population comprised patients who initiated avelumab plus axitinib as first-line therapy between December 20, 2019, and October 17, 2022.*

**Study population**

*This retrospective chart review will evaluate patient data derived from the existing medical records of all enrolled patients. All decisions regarding the clinical management and treatment of the patients are made by the investigator as part of standard care in a real-world setting and are not contingent upon the patient's participation in the study. Data will be collected at each study site (if available).*

*The study period will range from December 20, 2019, to October 31, 2022. Patients with an index date between December 20, 2019, and October 17, 2022, will be enrolled in this study. To ensure a two-week follow-up period, patients with an index date between December 20, 2019, and October 17, 2022, will be included. The two-week follow-up period is determined based on the dosing interval for avelumab, considering that the time of initiation of avelumab and axitinib may differ.*

*Index date: The date of the first prescription of avelumab plus axitinib combination therapy.*

*Observation period: Patients will be followed-up from the index date to October 31, 2022.*

※ The date of the first prescription of avelumab plus axitinib combination therapy is the administration start date of the drug initiated first.

**Data source**

*Considering the retrospective nature of the study, all data will be collected from patient medical records at the participating study sites.*

**Treatment/cohort labels**

Avelumab plus axitinib combination therapy

**2.2 STUDY OBJECTIVES****Primary objective**

PFIZER CONFIDENTIAL

CT24-WI-GL03-RF03 2.0 *Non-Interventional Statistical Analysis Plan For Secondary Data Collection*  
*Study 01-Jun-2020*  
*Page 5 of 30*

*To describe the demographic and clinical characteristics of Japanese patients with mRCC treated using avelumab plus axitinib as a first-line therapy in a real-world setting.*

Secondary objectives

- *To evaluate the treatment outcomes of avelumab plus axitinib as first-line therapy for patients with mRCC in a real-world setting, as determined by the following endpoints:*
  - *Real-world progression-free survival (PFS).*
  - *Overall survival (OS).*
  - *Objective response rate (ORR).*
  - *Best overall response (BOR) for primary lesions.*
  - *Time to treatment discontinuation (TTD) of avelumab plus axitinib as first-line therapy.*
- *To describe the treatment patterns for avelumab plus axitinib as first-line therapy in a real-world setting.*
- *To describe the clinical applicability of corticosteroids for immune-related adverse events (irAEs) occurring during the course of avelumab plus axitinib combination therapy.*
- *To describe the pre-treatment and treatment of infusion-related reactions caused by avelumab.*
- *To describe the subsequent treatment of avelumab plus axitinib combination therapy.*

CCI

### 3 HYPOTHESES AND DECISION RULES

#### 3.1 STATISTICAL HYPOTHESES

This study is not intended to test hypotheses.

#### 3.2 STATISTICAL DECISION RULES

A two-sided 95% confidence interval will be calculated for interval estimation. In addition, no multiplicity adjustment will be performed.

### 4 ANALYSIS SETS/POPULATIONS

#### 4.1 FULL ANALYSIS SET (FAS)

*The FAS will comprise patients who meet the inclusion criteria and do not meet the exclusion criteria.*

Inclusion criteria

- 1) *Diagnoses of mRCC based on the General Rule for Clinical and Pathological Studies on RCC (Fifth Edition) before the administration of avelumab plus axitinib*

PFIZER CONFIDENTIAL

as first-line therapy. Patients with *mRCC* presenting with unresectable disease, either a unresectable locally advanced or metastatic disease.

- 2) Age over 18 years at the time of the first administering of avelumab plus axitinib as first-line therapy for *mRCC* (baseline).
- 3) Index date from December 20, 2019, to October 17, 2022.

### **Exclusion criteria**

- 1) Patients participating in a prospective interventional clinical trial assessing an investigational product during the observational period.
- 2) Patients (or a patient's legal representative) refusing to provide patient data during the consent process.

### **4.2 SAFETY ANALYSIS SET**

Not applicable

### **4.3 OTHER ANALYSIS SET**

#### Efficacy analysis set

*The efficacy analysis set is a subset of the FAS comprising patients whose index date is prior to April 30, 2022, to ensure a 6-month follow-up period.*

### **4.4 SUBGROUPS**

*A subgroup analysis will be considered, including but not limited to the subgroups categorized by IMDC (International Metastatic RCC Database Consortium) risk group, age ( $\geq 75$  years or  $< 75$  years), and the administration of corticosteroid therapy for irAE in the medical record.*

## **5 ENDPOINTS AND COVARIATES**

#### Handling of data on the number of days

The number of days from the start date to the target date will be calculated as follows:

- The target date is earlier than the start date = Target date — Start date
- The target date is on or after the start date = Target date — Start date + 1

The number of days will be handled as follows:

- ✓ 1 week = 7 days
- ✓ 1 month = 30.4375 days
- ✓ 1 year = 365.25 days

In addition, missing data will be imputed with reference to "6. HANDLING OF MISSING VALUES."

### **5.1 EFFICACY/EFFECTIVENESS ENDPOINT(S)**

<Derivation of time-to-event variables>

Item	Derivation method
Real-world progression-free survival (PFS)	Defined as the period from the start date of avelumab plus axitinib combination therapy to

PFIZER CONFIDENTIAL

	
the date of first disease progression (clinical evaluation based on radiographic, clinical, and pathological examinations, as well as other evaluations by the principal investigator or co-investigator) or death from any cause, whichever occurs earlier. If there is no clinical record of death or disease progression, the following dates will be used for censoring, based on medical records:
 
 
(1) If first-line therapy is ongoing, the final progression-free confirmation date or the date of the last hospital visit, whichever is earlier, will be used for censoring.
 
(2) If second-line therapy has not been initiated after the end of first-line therapy, the final progression-free confirmation date or the date of the last hospital visit, whichever is earlier, will be used for censoring.
 
(3) If second-line therapy has been initiated, the date of initiating the second-line therapy will be used for censoring.
 
(4) If nephrectomy has been performed, the date of nephrectomy will be used for censoring.
 

Reasons for real-world PFS events	
Reasons for real-world PFS events are defined as follows:
 
"Disease progression after the initiation of avelumab plus axitinib combination therapy" will be selected if there was disease progression after starting avelumab plus axitinib combination therapy.
 
"Death" will be selected if the patient has died.

Reasons for censoring real-world PFS	
Reasons for censoring real-world PFS are defined as follows:
 
"No disease progression during or after first-line therapy" will be selected if first-line therapy is ongoing or if second-line therapy has not been initiated after the end of first-line therapy.
 
"Second-line therapy started" will be selected if second-line therapy has been initiated.
 
"Nephrectomy performed" will be selected if nephrectomy has been performed.

Overall survival (OS)	
Defined as the period from the initiation of avelumab plus axitinib combination therapy to the date of death from any cause. If there is no

PFIZER CONFIDENTIAL

CT24-WI-GL03-RF03 2.0 *Non-Interventional Statistical Analysis Plan For Secondary Data Collection*  
*Study 01-Jun-2020*  
 Page 8 of 30

	record of death, the date when the survival of the patient was last confirmed on record (date of last hospital visit) will be used for censoring.
Time to treatment discontinuation (TTD) of avelumab plus axitinib combination therapy as first-line therapy	Defined as the period from the date of initiation of avelumab plus axitinib combination therapy to the date of ending treatment* for any reason (excluding discontinuation due to efficacy). In the case of discontinuation due to efficacy, the date of last administration will be used for censoring. If treatment has not ended, the date of the last hospital visit will be used for censoring. * The end date of treatment is the date of last avelumab administration + 13 days or the date of last axitinib administration, whichever occurs later, or the data-cut date, if performed earlier.
TTD of avelumab as first-line therapy	Defined as the period from the date of initiation of avelumab to the date of ending administration* for any reason (excluding discontinuation due to efficacy). In the case of discontinuation due to efficacy, the date of the last avelumab administration will be used for censoring. If treatment has not ended, the date of the last hospital visit will be used for censoring. * The end date of avelumab therapy is the date of the last avelumab administration + 13 days or the data-cut date, whichever occurs earlier.
TTD of axitinib as first-line therapy	Defined as the period from the date of initiation of axitinib to the date of ending administration* for any reason (excluding discontinuation due to efficacy). In the case of discontinuation due to efficacy, the date of the last axitinib administration will be used for censoring. If treatment has not ended, the date of the last hospital visit will be used for censoring. * The end date of axitinib is the date of the last axitinib administration.
Reasons for the TTD event	Reasons for TTD event are defined as follows: Disease progression/adverse event/other (death)/other (excluding death)
Reasons for censoring TTD	Reasons for censoring TTD are defined as follows: "Treatment ongoing" will be selected if the treatment is ongoing.

PFIZER CONFIDENTIAL

CT24-WI-GL03-RF03 2.0 *Non-Interventional Statistical Analysis Plan For Secondary Data Collection*  
 Study 01-Jun-2020  
 Page 9 of 30

	" discontinuation due to efficacy " will be selected in case of discontinuation due to efficacy.
--	--

<Derivation of categorical variables>

Item	Derivation method
Objective response to avelumab plus axitinib combination therapy	Determination of the best overall response (tumor assessment) is categorized as follow: "Objective response" when "CR" or "PR." "Non-objective response" when "SD," "PD," or "NE".
Objective response of primary lesions	Determination of the best overall response (tumor assessment) is categorized as follow: "Objective response" when "CR" or "PR." "Non-Objective response " when "SD," "PD," or "NE."

CR, complete response; PR, partial response; PD, progressive disease; NE, not evaluable for response; SD, stable disease.

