9.2. Setting

This retrospective chart review will evaluate patient data derived from patient's existing medical records from the enrolled patients. All decisions regarding the clinical management and treatment of the patients are made by the investigator as part of standard care in a real-world setting and are not contingent upon the patient's participation in the study. Data will be collected at each study site (if available).

PFIZER CONFIDENTIAL

CT24-WI-GL02-RF02 4.0 Non-Interventional Study Protocol Template For Secondary Data Collection Study 01-Jun-2022

The study period is from 20 December 2019 to 31 October 2022. Patients with index date between 20 December 2019 and 17 October 2022 will be enrolled in this study. To ensure a 2 weeks follow up period, patients with an index date between 20 December 2019 and 17 October 2022 will be included in this study. The period of 2 weeks is determined based on the dosing interval for avelumab, in consideration of the fact that the start times of administration for avelumab and axitinib may differ.

- Index date: The date of first prescription of avelumab plus axitinib combination therapy.
- Observation period: Patients will be followed from the index date to 31 October 2022.

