9.3.1. Definition of clinical outcome measures

Real-world progression-free survival (PFS)

Real-world PFS is defined as the time from the start of treatment with avelumab plus axitinib to the date of first disease progression (as clinically assessed by a local investigator based on a radiology assessment, laboratory evidence, pathological data, and/or other assessments) or death due to any cause, which ever came first. If there are no clinical records of death or disease progression, patients will be censored at the date of initiation of the next line of therapy for those undertaking 2 or more lines of therapy based on the details in their medical records or at their last visit date during the study period for those undergoing only first line of therapy. However, if the nephrectomy is performed earlier than the above date, the data is to be treated as censored at the date of nephrectomy.

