### **Analysis of secondary objectives**

#### **7.2.2.2 Real-world progression-free survival**

Source : Efficacy analysis set  
 population  
 Endpoint : Real-world PFS  
 Analysis content : For the endpoint, the median and its 95% confidence interval will be calculated using the Kaplan–Meier method. In addition, the Kaplan–Meier curve will be plotted, and the PFS rate for every 12 months and its 95% confidence interval will be calculated. Greenwood’s formula will be used to calculate the confidence interval for the PFS rate. In addition, the number of event-onset cases and the number of censored cases will be presented. A frequency table (number of cases, percentage (%)) will be created, considering the reasons for the event and reasons for censoring. In order to evaluate the observation period, the median observation period and its 95% confidence interval will be calculated by estimating the reverse Kaplan-Meier curve in which censoring patients are regarded as patients with events and patients with events are regarded as censoring patients.

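### Real-world PFS is censored at second-line start or nephrectomy only in patients with no event on record, so censoring depends on what happens later

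*SAP*

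**What the plan says.** SAP 5.1 defines real-world PFS as the time from treatment start to first progression or death. One sentence then governs all censoring: "If there is no clinical record of death or disease progression, the following dates will be used for censoring". Four rules follow.

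- Rules (1) and (2) cover patients without second-line therapy. They use the last progression-free confirmation or the last visit, whichever is earlier.
- Rule (3): "If second-line therapy has been initiated, the date of initiating the second-line therapy will be used for censoring".
- Rule (4): "If nephrectomy has been performed, the date of nephrectomy will be used for censoring".

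The event definition does not stop at second-line start or surgery. The progression category "will be selected if there was disease progression after starting avelumab plus axitinib combination therapy", and death counts from any cause.

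Protocol 9.3.1 has the same precondition, after which "patients will be censored at the date of initiation of the next line of therapy for those undertaking 2 or more lines of therapy". It then adds: "However, if the nephrectomy is performed earlier than the above date, the data is to be treated as censored at the date of nephrectomy". The period in which an event can be recorded is set in protocol 9.2: "Observation period: Patients will be followed from the index date to 31 October 2022".

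Under SAP 7.2.2.2 the median is estimated by Kaplan-Meier and "the PFS rate for every 12 months and its 95% confidence interval will be calculated".

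**The concern.** Kaplan-Meier estimation needs the decision to censor a patient at a given time to rest on what is known by that time. Here, whether second-line start or nephrectomy is a censoring time is settled by looking ahead to the end of observation. That breaks the assumption by construction, even if switching has nothing to do with prognosis. The estimate then corresponds to neither rule a reader might assume, which are to censor everyone at the switch or to follow everyone through it.

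Real-world PFS is the first-listed treatment outcome, and protocol section 7 gives follow-up beyond 2 years as the reason for this study. Of the 12- and 24-month rates, the later one is distorted more. The planned table of censoring reasons will show how many patients were censored at a switch or surgery. It will not show how many events came after one, so a reader cannot undo the effect.

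A separate gap concerns precedence. Rules (1) to (3) exclude one another, but a patient with nephrectomy meets rule (4) and one of the other three. That gives two candidate dates and two censoring reasons, and the SAP does not say which applies.

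**Working it through.** The plan states no figure to reproduce. The check reads the rule literally and then sizes its effect.

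**1. Two patients.** Both start second-line therapy at month 8 without recorded progression. One progresses at month 14: there is a record of progression, so rule (3) is not reached, and this patient is an event at 14. The other is event-free to the end of observation: rule (3) applies, and this patient is censored at 8. Their histories are identical up to month 8.

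**2. Direction.** The estimate is the product of (1 − d/n) over event times. The SAP rule and the follow-through rule have the same recorded events d at the same times. The SAP rule has removed some event-free patients early, so its n is never larger. The SAP estimate therefore cannot exceed the follow-through estimate.

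**3. Worked example, no distribution assumed.** Take 100 patients followed to month 30. Twenty start second-line at month 8 without progression, and 10 of these progress at month 14. Of the other 80, 40 progress at month 14. PFS at 24 months is:

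- SAP rule: 10 censored at month 8, leaving 90 at risk and 50 events; 1 − 50/90 = 44.4%
- Follow everyone through: 1 − 50/100 = 50.0%
- Censor everyone at the switch: 1 − 40/80 = 50.0%

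**4. Simulation.** Inputs from the documents:

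- Median 13.8 months (trial cited in protocol section 7).
- Index dates 20 December 2019 to 29 April 2022 (efficacy analysis set) and observation to 31 October 2022. Potential follow-up is 185/30.4375 = 6.08 to 1046/30.4375 = 34.37 months.

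Assumptions: exponential PFS; uniform index dates; switch or nephrectomy at a constant hazard of 0.003, 0.005, 0.01 or 0.02 per month, independent of PFS; unchanged PFS hazard afterwards; all later events recorded. One million patients per scenario. True PFS is 2^(−12/13.8) = 54.7% at 12 months and 2^(−24/13.8) = 30.0% at 24 months.

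| Patients affected | Median (months) | 12-month PFS | 24-month PFS |
|---|---|---|---|
| 3.5% | 13.6 | 54.4% | 29.1% |
| 5.8% | 13.5 | 54.1% | 28.6% |
| 11% | 13.3 | 53.7% | 27.2% |
| 20% | 12.9 | 52.5% | 24.5% |
| Either uniform rule | 13.8 | 54.7% | 30.0% |

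Repeat runs agreed to within about 0.2 percentage points and 0.1 month. With a true median of 10 or 18 months and 20% affected, 24-month PFS was 14.4% against 18.9%, and 34.1% against 39.7%.

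**5. At the study's size.** The protocol expects about 150 patients in total; 130 in the efficacy set is assumed. The mean 24-month gap to follow-through was −1.4, −2.8 and −5.5 points at 5.8%, 11% and 20% affected, against a 95% CI half-width of about 10 points. In 12,000 replicates the SAP estimate never exceeded follow-through.

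**6. If progression after second-line start was not collected.** Deaths are still collected for OS and are PFS events. With deaths as the only post-switch events (assumed median 20 to 30 months after the switch, 11% affected), the SAP rule gives a 24-month PFS of about 27.7% to 28.4%, against 30.0%.

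**7. Precedence.** Protocol 9.3.1 orders nephrectomy against a preceding date; SAP 5.1 does not repeat this. The protocol's reference to that date can mean the censoring date alone, or the event date as well. On the second reading nephrectomy censors everyone and the protocol contradicts the SAP. For second-line start, both documents carry the outcome-dependent rule.

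**The case against.** The strongest objection is that the uniform rules recover the truth only if switching is unrelated to prognosis, which is doubtful for second-line therapy. Suppose 25% or 50% of switches were really unrecorded progressions, at the 0.01 hazard. The chance of a switch by month 24 is 1 − e^(−0.24) = 0.213, so true 24-month PFS is 30.0 × (1 − 0.25 × 0.213) = 28.4%, or 30.0 × (1 − 0.50 × 0.213) = 26.8%. The SAP rule gives about 27.2% in both cases (errors −1.2 and +0.4 points). Either uniform rule gives about 30.0% (errors +1.6 and +3.2). The criticised rule is closer in both. This stands as a limit on any claim about net direction. It does not defend the rule: one error happens to offset another, by an amount nobody can see in the output.

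Three further points stand in part.

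- The affected share is unknown, and at 6% to 11% the shift lies well inside the confidence interval. It is, however, systematic and does not shrink with more patients.
- The documents do not show whether progression after second-line start was collected. Step 6 shows that deaths alone leave a smaller effect, about 2 points.
- The nephrectomy part is weaker than the second-line part, because one reading of protocol 9.3.1 already gives a uniform rule and the protocol does supply an order among censoring dates. The SAP still has to say so.

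Finally, choosing between censoring at the switch and following through is a choice of question, and the documents do not settle it. That is a reason to state one and report the other.

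**Conclusion.** The concern holds: as written, the PFS censoring rule depends on later outcome, and no visible text in either document repairs it. Relative to following everyone through, the estimate can only be lower or equal. At a 13.8-month median, with switching independent of prognosis, the loss at 24 months is about 1 to 5.5 percentage points for 3.5% to 20% of patients affected, and on the median about 0.2 to 0.9 months. These sizes rest on an assumed share and on constant hazards; the mechanism does not. The direction relative to true PFS is not fixed if some switches conceal progression. The missing precedence for nephrectomy is a second, smaller defect, which could lead two programmers to different PFS times from the same data. This should be fixed before analysis. It does not touch the primary objective, which is to describe patient characteristics.

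**What to change.** In SAP 5.1, state one rule for every patient, whatever happens later. For example:

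> A PFS event is progression or death on or before the earlier of second-line start and post-index nephrectomy. Otherwise the patient is censored at the earlier of those two dates or, if neither occurred, at the date given by rule (1) or (2). The censoring reason is the one attached to the date used.

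Report the other uniform rule, which ignores second-line start and nephrectomy for all patients, as a sensitivity analysis as far as progression after second-line start was collected. If it was not, say so, because follow-through would then run high. Add a row to the PFS table with the number of events recorded after second-line start or nephrectomy. Align protocol 9.3.1 and state which date its nephrectomy sentence refers to.

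The cost is SAP wording, one protocol sentence, a few lines of derivation code and one table row. The main rule needs only progression, death, second-line and nephrectomy dates, all of which are within the planned data. The price is that some post-switch events leave the main analysis and that censoring at a switch may itself be informative; the sensitivity analysis and the added count let readers judge this.
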